6.3 RISK-BENEFIT ASSESSMENT

Febuxostat is approved in the European Union for the treatment of gout at dosages of 80 mg and 120 mg once a day, while the 120 mg strength has recently received marketing approval by the EC [8] for the prevention and treatment of hyperuricemia in adult patients undergoing chemotherapy for hematologic malignancies at intermediate to high risk of TLS. Therefore, the adult population participating to the present trial can benefit from an early access to an effective and safe treatment, whereas the pediatric population will be exposed to potential risk, which can be considered low taking into account the following evidences:

- 1) TLS is a life-threatening condition that may occur rapidly in children. Children hematologic malignancies are typically highly proliferative and highly chemosensitive. Thus, while chemotherapy may be strongly effective for them, it may also determine massive TLS with fatal outcomes. It is therefore essential to protect children with the best available and more suitable therapeutic strategy. It is worth noting that at the moment an oral age-appropriate formulation of allopurinol is not available in Europe. The present study is part of the febuxostat Pediatric Investigational Plan agreed with the Pediatric Committee of the EMA [32] and endorsed by the EMA [17].
- 2) A specific toxicology program has been run to fulfill the requirements of the febuxostat pediatric development [17]. In both adult and juvenile rats, dose-limiting toxicities were associated with obstructive nephropathies due to the precipitation of xanthine in urine. These findings are considered a consequence of species-specific purine metabolism and urine composition, and are deemed of no relevance for febuxostat clinical development. Indeed, the formation of xanthine crystals is not expected at the febuxostat dose levels recommended for adult humans and neither for children and adolescents from 6 to 17 years of age.
- 3) Febuxostat efficacy in the prevention/treatment of hyperuricemia in adult patients undergoing

chemotherapy for hematologic malignancies at intermediate to high risk of TLS was extensively proven by the FLORENCE study [30] and febuxostat 120 mg strength was recently approved for the prevention and treatment of hyperuricemia in this patient population (ADENURIC[®] SmPC Appendix II: EU SmPCs for adenuvic[®]).

4) Febuxostat safety profile in adults has been broadly explored in the gout and TLS experience. In the clinical development for the gout indication, more than 4000 subjects received at least one febuxostat dose; more than 2500 subjects were exposed to febuxostat 80 mg, and more than 1000 to febuxostat 120 mg; and the mean duration of dosing in the 80 mg and 120 mg groups was approximately 350 and 400 days, respectively. Febuxostat was safe and generally well tolerated at doses of 80 mg, 120 mg and 240 mg (two times the maximum clinical dose). Adverse drug reactions (ADRs) were mostly mild or moderate in severity. The worldwide post-marketing experience confirmed the safety of febuxostat in the gout and adult TLS setting [31]. In the phase III FLORENCE study [30] comparing febuxostat to allopurinol for the prevention of hyperuricemia in adult patients with hematologic malignancies at intermediate to high risk for TLS, 173 patients were exposed to febuxostat 120 mg for a mean time of approximately 7 days. No safety concerns raised from febuxostat treatment. Adverse drug reactions (ADRs) occurred with the same incidence of allopurinol (6.4%) and, noteworthy, all febuxostat ADRs were mild or moderate in severity. Neither serious ADRs, nor study drug-related deaths occurred.

5) The pediatric febuxostat doses were selected based on predicted exposures (C_{max} and AUC) which were considered to be safe (i.e., exposure not greater than that observed in adults receiving 240 mg dose in previous clinical studies), and efficacious (i.e., febuxostat exposure following a 120 mg dose to adults was effective in controlling sUA levels throughout the chemotherapy treatment period).

6) In order to reduce any risk or discomfort associated with blood sampling in children and adolescents, a population PK design allowing to minimize the number of blood samples has been adopted.

Finally, the potential risk for the pediatric population associated with the participation to this study is estimated low, also considering the sequential administration of the two different treatment doses per age group, while the expected benefit is predicted to be quite relevant. In fact, no major differences in the TLS diagnosis and management are present between adults and children, thus the superior reduction of sUA levels obtained by febuxostat in comparison to allopurinol in adults is highly expected to be confirmed in the pediatric population. The present PK/PD study has been designed to explore the PK/PD profile of febuxostat in the pediatric population in comparison to adults, and to possibly define the best dose, in terms of safety and efficacy, to be administered to children and adolescents, while avoiding/minimizing inappropriate exposure to non efficacious/non safe treatment, as per guideline CHMP/EWP/147013/2004 [33].

7. STUDY OBJECTIVES

7.1 PRIMARY OBJECTIVE

The primary objectives of this trial are:

- To assess the pharmacokinetics (PK) of febuxostat in pediatric patients ($\geq 6 < 18$ years of age) and in adults suffering from hematological malignancies at intermediate to high risk of TLS.
- To compare the febuxostat exposure in pediatric patients ($\geq 6 < 18$ years of age) with the one achieved in adults administered with a dose of 120 mg/QD.

7.2 SECONDARY OBJECTIVES

The secondary objectives of this trial are:

- To compare the pharmacodynamics (PD) of febuxostat between pediatric patients ($\geq 6 < 18$ years of age) and adults.
- To evaluate and compare the PK/PD relationship of febuxostat in pediatric patients ($\geq 6 < 18$ years of age) and adults.
- To evaluate the safety of febuxostat between pediatric patients ($\geq 6 < 18$ years of age) and adults.
- To evaluate the occurrence of Laboratory TLS (LTLS) and Clinical TLS (CTLs) according to Cairo and Bishop Criteria (see Appendix I: Definition of LTLS and CTLs).
- To assess the age-appropriate formulation acceptability in children.

8. INVESTIGATIONAL PLAN

8.1 OVERALL STUDY DESIGN AND PLAN DESCRIPTION

This trial is designed as an open label, multi-centre, parallel group study to be conducted in approximately 40 sites. A total of 120 patients are expected to be treated in this trial distributed in 3 age-cohorts: 48 children (aged 6 to less than 12 years), 48 adolescents (aged 12 to less than 18 years) [1] and 24 adults, suffering from hematological malignancies at intermediate to high risk of TLS, with no access to rasburicase, and scheduled to receive the first cycle of cytotoxic chemotherapy regardless of line of treatment. The evaluation of TLS risk will be based on the classification model issued by Cairo and co-workers and published in the British Journal of Haematology [4], as reported in Appendix III: TLS Risk Assessment.

Potential hematologic patients at intermediate to high risk of TLS will be assessed for eligibility at the Screening Visit, which should be held up to 1 week (+2 days of accepted timeframe window) prior to the Start of Treatment (Day -9 to Day 1). The Start of Treatment (Visit 1, Day 1) will be scheduled 2 days prior to the planned start of first chemotherapy cycle; Screening Visit and Visit 1 (Day 1) may coincide.

After confirmation that all inclusion and none of the exclusion criteria are met, eligible patients will receive oral administration of the following dose of febuxostat per age group:

- Children

Cohort 1: 40 mg once daily;

Cohort 2: 60 mg once daily.

- Adolescents

Cohort 3: 80 mg once daily;

Cohort 4: 120 mg once daily.

- Adults

120 mg once daily.

The two dose levels per children and adolescent groups will be sequentially administered to cohort. The first ≈ 24 children will receive the lower dose of 40 mg once daily and the first ≈ 24 adolescents the dose of 80 mg once daily. Afterwards, the higher doses will be administered: 60 mg once daily to children, and 120 mg once daily to adolescents. Cohort 1, Cohort 3 and adults treatments will start simultaneously. The control group of adult patients has been chosen to allow the comparison of PK/PD parameters between the pediatric ($\geq 6 < 18$ years) and the adult populations.

The final total number of patients/patients distributed in each age/dose cohort might slightly deviate

from the planned number since patients who satisfactory passed the screening have the right to be treated.

Treatment will start two days prior to the planned beginning of chemotherapy and will continue for 7 to 9 consecutive days, on the basis of chemotherapy duration that will be decided by the Investigator. A Follow Up/End of Study Visit (Visit 10, Day 14±2 days) will be performed for each patient at Day 14 (±2 days of accepted timeframe).

Overall, the study will include 10 to 11 pre-planned visits, depending on the selected hypouricemic treatment duration:

Screening Visit (Day -9 to Day 1)

NOTE: re-screening will be allowed but requires sponsor/medical monitor's approval. A patient may maximally re-screened once.

Visit 1 (Day 1): Start of Treatment

Visit 2 (Day 2) to Visit 7 (Day 7): Treatment Period

Visit 8 (Day 8): Evaluation Visit

Visit 9 (Day 9): Optional, in case of prolonged treatment

Visit 10 (Day 14±2): Follow-Up/End of Study Visit

Regardless of the selected hypouricemic treatment duration, the treatment period for the assessment of the primary endpoints will start at Visit 1 (Day 1), corresponding to the patient's baseline, and will terminate after seven days of hypouricemic treatment, which is expected to be five days following chemotherapy initiation.

The average duration of each patient participation in this trial will be of approximately 3 weeks.

8.2 DISCUSSION OF STUDY DESIGN, INCLUDING THE CHOICE OF CONTROL GROUP

The present phase I/II trial has been designed taking into account the relevant published literature, available scientific guidelines and recommendations, standard clinical practice and the results of the phase III FLORENCE study [30] in adults. The study has been designed in order to avoid/minimize inappropriate exposure to non efficacious/non safe febuxostat doses in the pediatric population, as per guideline CHMP/EWP/147013/2004 [33].

The study outline was part of the febuxostat Pediatric Investigational Plan (PIP) agreed with the Pediatric Committee of the European Medicines Agency [32] and endorsed by the EMA [17].

The primary objective of this phase I/II study is to assess the pharmacokinetics (PK) of febuxostat in

pediatric patients ($\geq 6 < 18$ years of age) in order to ascertain that the systemic exposure attained with the selected doses is comparable to that achieved in adults administered with a dose of 120 mg/QD. The secondary objectives are to compare the pharmacokinetic/pharmacodynamics (PK/PD) and safety of febuxostat between pediatric patients (≥ 6 and < 18 years) and adults. The required sample size encompasses approximately 24 patients per treatment dose in children and adolescents groups, and ≈ 24 patients in the adults group. The choice of the 120 mg once daily febuxostat dosage for adults resembles that already successfully and safely used in the phase III FLORENCE study [30], whereas two different febuxostat dosages, both expected to result in an exposure to febuxostat not exceeding that seen with 240 mg once daily in adults, will be tested in each pediatric subset of patients in order to allow a PK study of febuxostat in the target population.

The pharmacokinetic of febuxostat has been extensively investigated both in adult healthy subjects and in patients with hyperuricemia and gout. In general, febuxostat PK parameters estimated by population PK analyses in patients are consistent with those obtained from healthy subjects, indicating that healthy subjects are representative for PK assessment in the patient population with gout. Pharmacokinetic analyses in special populations demonstrated that dosage adjustment is not required in patients with mild or moderate renal impairment [29]. The investigation on the influence of covariates such as age, weight and gender on febuxostat PK, PD and safety were considered not clinically meaningful, suggesting no need of dose adjustment based on these parameters in adult patients [22]. These data were taken into account to optimize the sample size of the present study, as per guideline CHMP/EWP/147013/2004 [33]. According to the PK profile of febuxostat, the pharmacokinetics in adolescent patients is expected to be similar to the one in adults, whilst minor differences in the pharmacokinetics of children aged 6 to 11 years are expected.

To resemble the FLORENCE study outline [30] and the future clinical practice, patients with hematological malignancies who are scheduled to be treated with cytotoxic chemotherapy, regardless of the line of treatment, and at intermediate to high risk of TLS, will be screened. Eligible patients will receive treatment for 7 to 9 consecutive days, starting from 2 days prior to chemotherapy. Children and adolescents will be administered one out of the two dose levels of febuxostat, 40 or 60 mg for children, and 80 or 120 mg for adolescents. As for an extreme cautious approach, the two dose levels in children and adolescents will be sequentially administered (Cohort 2 after Cohort 1 and Cohort 4 after Cohort 3). The first ≈ 24 children will receive the lower dose of 40 mg once daily, and the first ≈ 24 adolescents the dose of 80 mg once daily. Afterwards, the higher doses will be administered: 60 mg once daily to children and 120 mg once daily to adolescents. Adults will receive 120 mg once daily in accordance to the treatment schedule previously adopted in the FLORENCE study [30]. No restriction will be applied to the enrolment of patients with different types of hematological malignancies, nor to the chemotherapy regimen with the exception of those including investigational products. The inclusion of

patients with hematological malignancies at intermediate to high risk of developing TLS is deemed appropriate considering the results of the FLORENCE study [30] and that patients at high TLS risk will be included only providing that they either have no access or have contraindications to rasburicase, and would be otherwise treated with allopurinol.

8.3 SELECTION OF STUDY POPULATION

After providing informed consent, the eligibility of patients to enter this study will be assessed based on inclusion and exclusion criteria that will be checked at Screening Visit (Day -9 to Day 1) and some of them at Visit 1 (Day 1). Patients will be included only if they meet all inclusion criteria (see section 8.3.1) and any of the exclusion criteria (see section 8.3.2).

8.3.1 Inclusion criteria

male and female children of 6 to less than 12 years of age, adolescents of 12 to less than 18 years of age and adults from 18 years:

- a. scheduled for first cytotoxic chemotherapy cycle, regardless of the line of treatment, because of hematologic malignancies, and
- b. at intermediate or high risk of TLS [4], and
- c. with serum uric acid (sUA) levels < 10 mg/dL at Visit 1 (Day 1), and
- d. with no access to rasburicase;

8.3.2 Exclusion criteria

1. patients known to be hypersensitive to febuxostat or to any of the components of the formulation;
- 

6. patients with severe renal insufficiency;
 7. patients with severe hepatic insufficiency;
 8. patients with diagnosis of Laboratory TLS (LTLS) or Clinical TLS (CTLTS) at Visit 1 (Day 1).
- 

8.3.3 Withdrawal of patients from therapy or assessment

Participation in the study is strictly voluntary and patients have the right to withdraw from the study at any time for any reasons without giving explanation. This will not affect their rights for future medical care. Patients may also be withdrawn at the Investigator's discretion or at specific Sponsor's request at any time.

Patients should not receive further study medication and will be withdrawn from the study (study termination) in case of medical emergency or necessity including but not limited to:

- adverse events with a possible, probable or certain drug-causality as per Investigator's judgment of severity grade ≥ 3 CTCAE version 4.03;
- appearance of skin rash or of any signs which may indicate allergic/hypersensitivity reactions (**NOTE**: in case of severe allergic/hypersensitivity reactions, febuxostat must not be re-started in patients at any time; for guidance please refer to the EU SmPC, Appendix III: TLS Risk

	120 mg oral film coated tablet.
--	---------------------------------

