9.3.4 Secondary analysis

- ***Pharmacodynamic endpoint:***

Area under plasma uric acid concentration curves (AUC sUA_{1-8}) from baseline (Visit 1, Day 1) to the Evaluation Visit (Visit 8, Day 8) will be computed for dose and age group using a trapezoidal rule which approximates the integral or the area under a curve.

A graphic example is provided in order to show which is the area considered to calculate AUC.

Figure 1

The trapezoidal rule is a numerical method to be used to approximate the integral or the area under a curve. Trapezoidal rule first involves dividing the area into a number of strips of equal width, with low limit identified with a and upper limit with b. Then, approximating the area of each strip by the area of the trapezium formed and summing these approximations, the final numerical result will be the area under the curve.

The trapezoidal rule will be presented by mean of a definite integral:

$$\int_a^b f(x)dx$$

Last observation carried forward method (LOCF) will be applied for patients who discontinued the study prematurely and a linear interpolation method will be used to impute the missing data between visits.

The pharmacodynamic analysis will be run on PK population and for exploratory reasons on ITT population.

- ***PK/PD endpoint:***

Observed exposure-response data will be descriptively and graphically summarized by age and dose group.

The aim of this analysis is to support the assumption of a comparable PK/PD relationship between pediatric patients ($\geq 6 < 18$ years of age) and adults and to evaluate if potential deviations in PK are clinically relevant.

This analysis will be conducted on the PK population.

- ***Clinical endpoints: Incidence of LTLS and CTLS***

- The assessment for LTLS from Start of Chemotherapy (Visit 3, Day 3) to the Evaluation Visit (Visit 8, Day 8) will be defined as:

1: PRESENCE 2 or more laboratory abnormalities including: a 25% increase or levels above normal for serum uric acid, potassium, and phosphate or a 25% decrease or levels below normal for calcium.

0: ABSENCE less than 2 laboratory abnormalities including: a 25% increase or levels above normal for serum uric acid, potassium, and phosphate or a 25% decrease or levels below normal for calcium.

- The assessment for CTLS from Start of Chemotherapy (Visit 3, Day 3) to the Evaluation Visit (Visit 8, Day 8) is defined as:

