1: PRESENCE presence of LTLS in addition to 1 or more of the following significant clinical complications: renal insufficiency, cardiac arrhythmias, sudden death and seizures.

0: ABSENCE absence of LTLS or absence of any significant clinical complications: renal insufficiency, cardiac arrhythmias, sudden death and seizures.

Chi Square test will be used to compare statistically the rate incidence of LTLS and CTLS by dose and age group.

The efficacy analyses will be run on the ITT population and for exploratory reasons on PP-population.

- ***Assessment of the age-appropriate formulation acceptability***

Assessment of the age-appropriate formulation acceptability will be evaluated through a 5-point

hedonic scale anchored with the word super bad and super good and summarized by means of descriptive statistics by febuxostat dose in children. The analysis will be conducted on the safety population.

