9.3.7 Data imputations

Overall, the missing value will not be imputed because an observed cases approach will be used.

For AUC sUA calculation the last observation carried forward method (LOCF) will be applied for patients who discontinued the study prematurely and a linear interpolation method will be used to impute the missing data between visits.

[figure not shown]

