Report specific changes for relevant protocol section (including paragraph number and pages), additions should be highlighted as underlined, whereas deletions as ~~strike-out~~, reporting whenever possible the full affected changes. Alternatively, the tracked changes can be strictly limited to the affected lines.

▪ Amendment to Protocol Section 2 and Section 8:

Current version (page 4/18 and 45/72):

Section 2 Protocol Synopsis Exclusion Criteria (page 7) and Section 8.3.2 Exclusion Criteria (page 49) is amended as described below:

...

- patients with severe renal insufficiency~~;~~, as defined below calculated based on local clinical practice:
 - adult patients with a clearance creatinine < 30 mL/min;
 - pediatric patients with eGFR <60 mL/min/1.73 m².

...

Section 8.3.3 Withdrawal of patients from therapy or assessment (page 49/50) is amended as described below:

....

Patients should not receive further study medication and will be withdrawn from the study (study termination) in case of medical emergency or necessity including but not limited to:

- adverse events with a possible, probable or certain drug-causality as per Investigator's judgment of severity grade ≥ 3 CTCAE version 4.03;
- appearance of skin rash or of any signs which may indicate allergic/hypersensitivity reactions (**NOTE**: in case of severe allergic/hypersensitivity reactions, febuxostat must not be re-started in patients at any time; for guidance please refer to the EU SmPC, Appendix II:TLS Risk Assessment);
- severe hepatic insufficiency;
- severe renal insufficiency;
NOTE: renal insufficiency defined as below:
 - adult patients with a clearance creatinine < 30 mL/min;
 - pediatric patients with eGFR < 60 mL/min/1.73 m².

.....

SIGNATURES

The signatories have read the clinical trial protocol amendment No. 2 dated 03 Feb 2017 to the clinical trial protocol titled "*Open label, multi-centre, parallel group study to compare the pharmacokinetics (PK), pharmacodynamics (PD) and safety of febuxostat between pediatric patients ($\geq 6 < 18$ years of age) and adults*" - Final Version 1.0, dated 12 Apr 2016 - carefully and agree to adhere to its provisions.

SPONSOR's Representative

Signature

Date

Co-ordinating Investigator

PRINCIPAL INVESTIGATOR'S STATEMENT

a) Clinical Statement

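### Stopping study drug also ends study participation, so uric acid and TLS follow-up to Day 8 can be cut short for a reason related to the outcome, and the coding of an incomplete TLS window is undefined

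*Combined protocol and SAP*

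**What the plan says.** Section 8.3.3 has a single rule: "Patients should not receive further study medication and will be withdrawn from the study (study termination". The reasons include "adverse events with a possible, probable or certain drug-causality as per Investigator's judgment of severity grade ≥ 3 CTCAE version 4.03" and signs of hypersensitivity; the list then breaks off in the available text. The excerpt of 8.3.3 in Amendment No. 2, submitted for Hungary, repeats the rule and shows two further reasons, severe hepatic insufficiency and "severe renal insufficiency". It defines the latter as creatinine clearance below 30 mL/min in adults and eGFR below 60 mL/min/1.73 m² in paediatric patients.

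The flow chart (2.2) and the visit schedule (8.6.1) contain no early-termination visit. They give no instruction to keep sampling a patient who has stopped drug.

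On missing data, section 9.3.7 says: "For AUC sUA calculation the last observation carried forward method (LOCF) will be applied for patients who discontinued the study prematurely". Section 9.3.4 says the same, and gaps between visits are interpolated. For everything else, 9.3.7 applies an observed-cases approach without imputation.

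Section 9.3.4 codes laboratory TLS (LTLS) and clinical TLS (CTLS) as 1 or 0 over Day 3 to Day 8. CTLS needs LTLS plus at least one of "renal insufficiency, cardiac arrhythmias, sudden death and seizures". The rates are compared by chi-square on the ITT set, which 9.2 defines as everyone allocated a treatment box. There is no code for a window observed only in part.

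**The concern.** Stopping a drug and stopping observation are separate decisions, and here the first triggers the second. Three consequences follow if the text is applied as written.

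First, loss of TLS follow-up can depend on the outcome. Severe renal insufficiency is a reason to leave. Renal insufficiency is a component of CTLS, and Appendix III treats renal dysfunction as raising the TLS risk class. A patient who leaves for renal failure before meeting the LTLS criteria is unobserved while at raised risk.

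Second, AUC sUA1-8 carries an on-drug value over off-drug days. The endpoint is secondary, but section 6.1 relies on it because it matches the primary efficacy parameter of the adult phase III study.

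Third, truncation can differ between the groups being compared. The Amendment No. 2 renal definition differs between adults and paediatric patients. I take no view on those thresholds. The point is only that, while meeting one ends data collection, different thresholds can shorten follow-up differently by age.

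**Working it through.** The plan gives no withdrawal rate and no figure on this point. Its group size is consistent: 5 groups × 24 = 120, as in 9.1. The sizes below are illustrations. The adult febuxostat figures come from the phase III results in the appended 120 mg SmPC, section 5.1: LTLS 8.1%; AUC sUA1-8 mean 514.0, SD 225.71 mg·h/dL. Later TLS risk, numbers stopping and uric acid levels after the stop are my assumptions.

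**TLS incidence.** Expected LTLS events per group: 24 × 0.081 = 1.9. One patient is 1/24 = 4.2 percentage points. Let k of 24 patients stop event-free, with later risk q, and let the others have risk 0.081.

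- Full follow-up: [0.081 × (24 − k) + k × q] / 24
- Stopped patients coded 0: 0.081 × (24 − k) / 24
- Stopped patients excluded: 0.081

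| k | q | Full follow-up | Coded 0 | Excluded |
|---|---|---|---|---|
| 2 | 8.1% | 8.1% | 7.4% | 8.1% |
| 2 | 25% | 9.5% | 7.4% | 8.1% |
| 2 | 50% | 11.6% | 7.4% | 8.1% |
| 4 | 25% | 10.9% | 6.8% | 8.1% |
| 4 | 50% | 15.1% | 6.8% | 8.1% |

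For example, with k = 2 and q = 25%: (0.081 × 22 + 0.5)/24 = 2.282/24 = 9.5%. Exclusion is unbiased only when later risk is not raised. Coding as 0 understates the rate in every row. The two readings give different answers, so the rule has to be written down. A patient stopped before Day 3 is the extreme case: in the ITT set with no assessment inside the window, because 8.6.4 schedules none between Day 1 and Day 3.

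**AUC sUA1-8.** Average level: 514/168 h = 3.06 mg/dL, taken as the last value before the stop. If uric acid then moves linearly to S on Day 8, LOCF misses h × (S − 3.06)/2, where h = (8 − stop day) × 24.

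- Stop on Day 5, S = 8: 72 × 4.94/2 = 178 mg·h/dL for that patient.
- S from 3.06 to 10: 0 to 333 (Day 4 stop), 0 to 250 (Day 5), 0 to 167 (Day 6).
- Group mean, Day 5 stop with S = 8: 178 × 1/24 = 7 for one patient, 178 × 4/24 = 30 for four.
- A step instead of a slope, stop on Day 3 and level 2 to 3 mg/dL higher for 120 h: 240 to 360 for the patient, or 10 to 15 on the group mean for one patient.

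The standard error of a 24-patient mean is 225.71/√24 = 46. One patient therefore shifts the mean by 7/46 to 15/46, about 0.2 to 0.3 standard errors, and four patients in the Day 5 case by 30/46 = 0.6. The most extreme combination run, four patients stopping on Day 4 with S = 10, gives 333 × 4/24 = 56, or 1.2. If S falls below 3.06, for instance because another urate-lowering drug is started, the sign reverses.

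**The case against.** The strongest case against has four parts.

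**Text is missing.** The end of 8.3.3 is not shown, Amendment No. 2 reproduces only an excerpt, and section 8.7.8 on adverse event follow-up appears in the contents but not in the text. A follow-up rule there cannot be excluded. This stands, so the point is limited to what the visible text requires. A reader might also infer that the LOCF rule proves no later values are expected after a drug stop. It does not, because it covers every premature discontinuation, including withdrawn consent.

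**TLS is not scored as absent.** A reader might infer that patients who leave are counted as event-free. The documents do not say so: 9.3.7 indicates observed cases, and the 1/0 coding is silent. This stands; the defect is an undefined rule.

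**Safety data are not shown to be lost.** A reader might infer that the Day 14 visit disappears for patients who stop. Section 8.1 says it is performed for each patient, 8.7.2 allows adverse events learned of later to be recorded, and treated patients stay in the safety population. This stands, although how 8.1 fits with study termination needs a sentence.

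**The affected patients may be few, and some are already counted.** A patient stopped for renal failure who already meets the LTLS and creatinine criteria is a CTLS case. The other visible reasons are toxicity or hepatic failure, so it is inference to say that the highest-risk patients are removed. Section 6.3 reports that febuxostat reactions in the adult study were all mild or moderate. That is a different scale from CTCAE, but it suggests few drug-related grade 3 stops. This lowers the expected size without removing the mechanism.

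Finally, uric acid after a stop may reflect another drug, since the ban in 8.5.5 need not apply once the patient has left. Putting such values in the main AUC is a choice of estimand, not a correction.

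**Conclusion.** The point holds in a limited form. The visible plan ties stopping drug to leaving the study, does not require uric acid or TLS assessment to Day 8 afterwards, completes AUC sUA1-8 by LOCF, and leaves an incomplete TLS window without a rule. Because one stopping reason is related to the renal part of CTLS, TLS incidence may be understated. With about two LTLS events expected per group, even one missed event is material to a group's rate. The likely effect on mean AUC sUA is small, about 0.2 to 0.3 standard errors for one patient, and its direction is not fixed. How often this happens cannot be derived from the documents. The primary analysis, a descriptive PK comparison, is not affected by the LOCF or TLS rules. The change is worth making because it is cheap, not because a large bias has been shown. Confidence is moderate, given the unseen parts of 8.3.3 and 8.7.8.

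**What to change.** - In 8.3.3, separate stopping study drug from ending data collection. Unless consent is withdrawn, continue the scheduled local TLS panel and central sUA to Day 8.
- Confirm there that adverse events and safety tests continue to the Day 14 visit, in line with 8.1.
- In 9.3.4, count TLS events over the full Day 3–8 window from the observed data, whether or not drug was stopped. State how a window that is still incomplete is coded, and report the number of such patients by age and dose group.
- Add a sensitivity analysis of AUC sUA1-8 that uses observed values after the stop instead of LOCF, flagging patients given another urate-lowering drug.

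The cost is protocol and analysis-plan wording plus a few central samples, at visits that already exist in the schedule. The drawback is that some uric acid values will reflect other treatment, which is why they belong in a sensitivity analysis. The criteria for stopping treatment are untouched. If the unseen parts of 8.3.3 or 8.7.8 already require this follow-up, the sections need only be aligned.
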